#### 4.1.4 Concomitant Therapy

4.1.4.1 No other cancer chemotherapy, radiotherapy, or immunomodulating agents will be used.

4.1.4.2 Medications that are strong inhibitors or inducers of CYP3A4 should be avoided (see [Appendix II](#)). Corticosteroids may induce CYP3A4 and are therefore not routinely recommended on study unless deemed absolutely necessary or when used in stable or decreasing doses from the time of study enrollment.

4.1.4.3 In vitro data indicate that XL184 is an inhibitor of P-glycoprotein (P-gp) transport activity. Co-administration of XL184 with a P-gp substrate may result in an increase in P-gp substrate plasma concentration. Therefore, use

caution when administering XL-184 with drugs known to be P-gp substrates (e.g., fexofenadine, aliskiren, ambrisentan, digoxin, colchicine, maraviroc, posaconazole, tolvaptan, etc.). XL184 is also a substrate of drug transporter MRP2, which may result in an increased plasma concentration of XL184 when administered with an inhibitor of MRP2. Use caution and monitor adverse events when administering XL184 with MRP2 inhibitors such as cyclosporine, delavirdine, efavirenz, and emtricitabine

- 4.1.4.4 The use of enzyme inducing anticonvulsants is not permitted. See [Appendix VII](#) for a list of unacceptable enzyme inducing and recommended non-enzyme inducing anticonvulsants.
- 4.1.4.5 XL184 has been associated with prolonged QTc, so medications that prolong or may prolong QTc should be avoided when possible (see [Appendix VIII](#)). If other medications that prolong QTc or may prolong QTc have to be used concomitantly, then QTc should be carefully monitored.
- 4.1.4.6 XL184 is highly protein bound (99.9%). Use caution when coadministering XL184 with medications that are highly protein-bound (e.g., diazepam, furosemide, dicloxacillin, and propranolol).
- 4.1.4.7 Patient drug information handout and wallet card should be provided to patients on study, see [Appendix X](#).

4.1.5 Study Specific Supportive Care:

Appropriate antibiotics, blood products, antiemetics, fluids, electrolytes and general supportive care are to be used as necessary. See [Section 4.1.4](#) for drugs that should not be used concomitantly due to potential interactions with XL184.

Diarrhea is a common side effect of XL184. Loperamide should be used at the first sign of significant diarrhea (See [Appendix VI](#)).

Palmar-plantar erythrodysesthesia syndrome (PPE; also known as hand-foot syndrome) is a common side effect of XL184. Careful attention should be paid to skin exams and supportive care instituted early if any swelling or erythematous skin changes or symptoms of pain or burning/tingling are noted. Patients should be instructed to apply moisturizing creams, avoid any trauma, harsh chemicals and limit hot water exposure. Topical steroid creams may be used and consider early dermatology referral.

Growth factors that support platelet or white cell number or function can only be administered for culture proven bacteremia or invasive fungal infection. The Study Chair should be notified before growth factors are initiated.

Patients should not have elective surgical procedures while on therapy. For patients who require emergent or urgent procedures, therapy may not be restarted until 28 days after major procedures and 7 days after minor procedures such as line replacement (3 days for external lines [e.g. Hickman or Broviac]).

For COG Supportive Care Guidelines see:  
[https://members.childrensoncologygroup.org/prot/reference\\_materials.asp](https://members.childrensoncologygroup.org/prot/reference_materials.asp) under  
Standard Sections for Protocols.

**4.2 Cycle 1**

4.2.1 Therapy Delivery Map – Cycle 1 This Therapy Delivery Map (TDM) relates to Cycle 1. Each cycle lasts 28 days.	_____
	Patient COG ID number
	DOB

Criteria to start each cycle are listed in [Section 3.2.7](#). Extensive treatment details are in [Section 4.2.3](#). This TDM is on 1 page.

DRUG	ROUTE	DOSAGE	DAYS	IMPORTANT NOTES
XL184 (cabozantinib)	PO	40 mg/m  /day	1-28	See Appendix IV for dosing nomogram. The cumulative weekly dose is 280 mg/m  . XL184 should be taken at approximately the same time each day on an empty stomach; patients should fast 2 hours before and 1 hour after taking the drug.

Ht \_\_\_\_\_ cm      Wt \_\_\_\_\_ kg      BSA \_\_\_\_\_ m^2

Date Due	Date Given	Day	XL184 _____ mg	Studies
			Enter calculated dose above and actual dose administered below	
		1	_____ mg	a-n
		2	_____ mg	
		3	_____ mg	
		4	_____ mg	
		5	_____ mg	
		6	_____ mg	
		7	_____ mg	
		8	_____ mg	a
		9	_____ mg	
		10	_____ mg	
		11	_____ mg	
		12	_____ mg	
		13	_____ mg	
		14	_____ mg	
		15	_____ mg	a, c, d, k
		16	_____ mg	
		17	_____ mg	
		18	_____ mg	
		19	_____ mg	
		20	_____ mg	
		21	_____ mg	
		22	_____ mg	a, m
		23	_____ mg	
		24	_____ mg	
		25	_____ mg	
		26	_____ mg	
		27	_____ mg	
		28	_____ mg	g, i, k

See [Section 5.0](#) for Dose Modifications for Toxicities and the COG Member website for Supportive Care Guidelines.

#### 4.2.2 Required Observations in Cycle 1

**All baseline studies must be performed prior to starting protocol therapy unless otherwise indicated below.**

- a. Hx/PE with VS including BP. Prior to Cycle 1 and weekly during Cycle 1. Please see [Section 5.5](#) for additional guidance regarding BP.
- b. Wt/Ht/Performance status.
- c. CBC/diff/platelets. Prior to Cycle 1 and every 2 weeks during Cycle 1.
- d. Electrolytes, BUN, creatinine, Ca++, PO4, Mg++, AST, ALT, bilirubin, albumin, urinalysis, amylase, lipase. Prior to Cycle 1 and every 2 weeks during Cycle 1. See [Section 5.4](#) for dose modifications due to proteinuria.
- e. TSH. Patients found to have an abnormal TSH level should have a free T4 level measured. Patients who enter the study on thyroid replacement should have their medication adjusted to maintain TSH in the normal range.
- f. PT/INR/APTT.
- g. ECG including QTc interval. Prior to Cycle 1 and at the end of Cycle 1.
- h. Tumor disease evaluation. Prior to Cycle 1.
- i. CEA, calcitonin (for patients with MTC only). Prior to Cycle 1 and at the end of Cycle 1. Calcitonin measurements should be obtained in the fasting state.
- j. X-ray tibial growth plate. Prior to start of therapy in all patients ≤ 18 years of age at enrollment. See [Section 5.10.1](#) for details.
- k. Patient diary. Every other week during Cycle 1. For patient diary see [Appendix III](#).
- l. Pharmacodynamics. See [Section 7.2.2](#) for details.
- m. Pharmacokinetics. Cycle 1. See [Section 7.2.1](#) for details.
- n. Pregnancy test. Female patients of childbearing potential require a negative pregnancy test prior to the start of each cycle; sexually active patients must use an acceptable method of birth control.

**This listing only includes evaluations necessary to answer the primary and secondary aims. OBTAIN OTHER STUDIES AS REQUIRED FOR GOOD CLINICAL CARE.**

#### Comments

(Include any held doses, or dose modifications)

#### 4.2.3 Treatment Details: Cycle 1

One cycle of XL184 treatment is described below. A cycle may be repeated every 28 days if the patient has at least stable disease and has again met laboratory parameters as defined in the eligibility [Section 3.2.7](#).

##### **XL184: PO**

Days: 1-28

Dose: 40 mg/m^2/day

Dosing will be performed based on body surface area (BSA), and rounded to the nearest 20 mg using the dosing nomogram (see [Appendix IV](#)). The cumulative weekly dose is 280 mg/m^2. Treatment will continue until tumor progression or unacceptable toxicity.

XL184 will be administered orally at approximately the same time each day.

Drug doses should be adjusted based on the BSA calculated from height and actual body weight measured within 7 days prior to the beginning of each cycle, and according to the dosing nomogram (see [Appendix IV](#)). Sites will fill out the number of prescribed tablets per day in the patient diary (see [Appendix III](#)). Patients must complete the patient diary with the date, time and number of XL184 tablets taken each day. The patient diary should be reviewed every 2 weeks during Cycle 1.

If a patient vomits after the dose of XL184 is administered, the dose should not be repeated. The tablet should be taken with a large glass of water on an empty stomach, and patient should not eat 2 hours before or 1 hour after each dose of XL184. The tablet should not be crushed or broken. Furthermore, a missed dose should not be taken within 12 hours of the next dose.

Patients should not eat grapefruit or drink grapefruit juice while being treated with XL184.

A note should be made in the patient diary if any of the above events take place.

See [Section 5.0](#) for Dose Modifications based on Toxicities.

Following completion of cycle, the next cycle starts on Day 29 or when starting criteria are met (see [Section 3.2.7](#)), whichever occurs later.

**4.3 Cycles 2 & 3**

**4.3.1 Therapy Delivery Map – Cycles 2 & 3**

This Therapy Delivery Map (TDM) relates to Cycles 2 and 3. Each cycle lasts 28 days. Treatment may continue in the absence of disease progression or unacceptable toxicity. Use a copy of this page once for Cycle 2 and once for Cycle 3 (please note cycle number below).

\_\_\_\_\_  
Patient COG ID number

\_\_\_\_\_  
DOB

Criteria to start each cycle are listed in [Section 3.2.7](#). Extensive treatment details are in [Section 4.3.3](#). This TDM is on 1 page.

DRUG	ROUTE	DOSAGE	DAYS	IMPORTANT NOTES
XL184 (cabozantinib)	PO	40 mg/m  /day	1-28	See Appendix IV for dosing nomogram. The cumulative weekly dose is 280 mg/m  . XL184 should be taken at approximately the same time each day on an empty stomach; patients should fast 2 hours before and 1 hour after taking the drug.

Enter Cycle #: \_\_\_\_\_ Ht \_\_\_\_\_ cm Wt \_\_\_\_\_ kg BSA \_\_\_\_\_ m^2

Date Due	Date Given	Day	XL184 _____ mg	Studies
			Enter calculated dose above and actual dose administered below	
		1	_____ mg	a-e, g, i, j
		2		
		3		
		4		
		5		
		6		
		7		
		8		
		9		
		10		
		11		
		12		
		13		
		14		
		15		a, c, d
		16		
		17		
		18		
		19		
		20		
		21		
		22		
		23		
		24		
		25		
		26		
		27		
		28	_____ mg	f # , h, k # , l #

#Cycle 2 only. See [Section 5.0](#) for Dose Modifications for Toxicities and the COG Member website for Supportive Care Guidelines.

**Cycles 2 & 3**

4.3.2 Required Observations in Cycles 2 &3

- a. Hx/PE with VS including BP. Every 2 weeks. Please see [Section 5.5](#) for additional guidance regarding BP.
- b. Wt/Ht/Performance status. Day 1 of each Cycle.
- c. CBC/diff/platelets. Every 2 weeks.
- d. Electrolytes, BUN, creatinine, Ca++, PO4, Mg++, AST, ALT, albumin, bilirubin, urinalysis, amylase, lipase. Every 2 weeks. See [Section 5.4](#) for dose modifications due to proteinuria.
- e. TSH. Day 1 of each cycle. Patients found to have an abnormal TSH level should have a free T4 level measured. See [Section 5.10.2](#) for details and management of thyroid toxicity.
- f. ECG including QTc interval. End of Cycle 2.
- g. X-ray tibial growth plate. Prior to Cycle 2 in patients with open growth plates, follow-up plain radiographs of the same growth plate(s) should be obtained. See [Section 5.10.1](#) for details and management of growth plate toxicity.
- h. Patient diary. End of each cycle. For patient diary see [Appendix III](#).
- i. Pharmacodynamics. Prior to Cycles 2 and 3. See [Section 7.2.2](#) for details.
- j. Pregnancy test. Female patients of childbearing potential require a negative pregnancy test prior to the start of each cycle; sexually active patients must use an acceptable method of birth control.
- k. Tumor disease evaluation. End of Cycle 2. Tumor Disease Evaluation should be obtained on the next consecutive cycle after initial documentation of either a PR or CR. Please note that for solid tumor patients, if the institutional investigator determines that the patient has progressed based on clinical or laboratory evidence, he/she may opt not to confirm this finding radiographically.
- l. CEA, calcitonin (for patients with MTC only). End of Cycle 2. Calcitonin measurements should be obtained in the fasting state.

**This listing only includes evaluations necessary to answer the primary and secondary aims. OBTAIN OTHER STUDIES AS REQUIRED FOR GOOD CLINICAL CARE.**

**Comments**  
(Include any held doses, or dose modifications)

#### 4.3.3 Treatment Details: Cycles 2 & 3

One cycle of XL184 treatment is described below. A cycle may be repeated every 28 days if the patient has at least stable disease and has again met laboratory parameters as defined in the eligibility [Section 3.2.7](#).

##### **XL184: PO**

Days: 1-28

Dose: 40 mg/m^2/day

Dosing will be performed based on body surface area (BSA), and rounded to the nearest 20 mg using the dosing nomogram (see [Appendix IV](#)). The cumulative weekly dose is 280 mg/m^2. Treatment will continue until tumor progression or unacceptable toxicity.

XL184 will be administered orally at approximately the same time each day as prescribed.

Drug doses should be adjusted based on the BSA calculated from height and actual body weight measured within 7 days prior to the beginning of each cycle, and according to the dosing nomogram (see [Appendix IV](#)). Sites will fill out the number of prescribed tablets per day in the patient diary (see [Appendix III](#)). Patients must complete the patient diary with the date, time and number of XL184 tablets taken each day. The patient diary should be reviewed after completion of each treatment cycle.

If a patient vomits after the dose of XL184 is administered, the dose should not be repeated. The tablet should be taken with a large glass of water on an empty stomach, and patient should not eat 2 hours before or 1 hour after each dose of XL184. The tablet should not be crushed or broken but be swallowed whole. Furthermore, a missed dose should not be taken within 12 hours of the next dose.

Patients should not eat grapefruit or drink grapefruit juice while being treated with XL184.

A note should be made in the patient diary if any of the above events take place.

See [Section 5.0](#) for Dose Modifications based on Toxicities.

Following completion of cycle, the next cycle starts on Day 29 or when starting criteria are met (see [Section 3.2.7](#)), whichever occurs later.

**4.4 All Subsequent Cycles**

**4.4.1 Therapy Delivery Map – All Subsequent Cycles**

This Therapy Delivery Map (TDM) relates to all subsequent cycles. Each cycle lasts 28 days. Treatment may continue in the absence of disease progression or unacceptable toxicity. Use a copy of this page once for each cycle (please note cycle number below).

\_\_\_\_\_  
Patient COG ID number

\_\_\_\_\_  
DOB

Criteria to start each cycle are listed in [Section 3.2.7](#). Extensive treatment details are in [Section 4.4.3](#). This TDM is on 1 page.

DRUG	ROUTE	DOSAGE	DAYS	IMPORTANT NOTES
XL184 (cabozantinib)	PO	40 mg/m  /day	1-28	See Appendix IV for dosing nomogram. The cumulative weekly dose is 280 mg/m  . XL184 should be taken at approximately the same time each day on an empty stomach; patients should fast 2 hours before and 1 hour after taking the drug.

Enter Cycle #: \_\_\_\_\_ Ht \_\_\_\_\_ cm Wt \_\_\_\_\_ kg BSA \_\_\_\_\_ m^2

Date Due	Date Given	Day	XL184 ____ mg	Studies
			Enter calculated dose above and actual dose administered below	
		1	_____ mg	a-e, (f-h)*, i # , k
		2		
		3		
		4		
		5		
		6		
		7		
		8		
		9		
		10		
		11		
		12		
		13		
		14		
		15		
		16		
		17		
		18		
		19		
		20		
		21		
		22		
		23		
		24		
		25		
		26		
		27	↓	
		28	_____ mg	j

\*Prior to Cycle 5 and 7, and every 3rd cycle thereafter. #Prior to Cycle 5 and every 6 cycles thereafter. See [Section 5.0](#) for Dose Modifications for Toxicities and the COG Member website for Supportive Care Guidelines.

**4.4.2 Required Observations in All Subsequent Cycles**

- a. Hx/PE with VS including BP. Day 1 of each cycle. Please see [Section 5.5](#) for additional guidance regarding BP.
- b. Wt/Ht/Performance status. Day 1 of each cycle.
- c. CBC/diff/platelets. Day 1 of each cycle.
- d. Electrolytes, BUN, creatinine, Ca++, PO4, Mg++, bilirubin, AST, ALT, albumin, urinalysis, amylase, lipase. Day 1 of each cycle. See [Section 5.4](#) for dose modifications due to proteinuria.
- e. TSH. Day 1 of each cycle. Patients found to have an abnormal TSH level should have a free T4 level measured. See [Section 5.10.2](#) for details and management of thyroid toxicity.
- f. ECG including QTc interval. Prior to Cycle 5 and 7 and then every 3rd cycle.
- g. Tumor disease evaluation. Prior to Cycle 5 and 7 and then every 3rd cycle. Tumor Disease Evaluation should be obtained on the next consecutive cycle after initial documentation of either a PR or CR. Please note that for solid tumor patients, if the institutional investigator determines that the patient has progressed based on clinical or laboratory evidence, he/she may opt not to confirm this finding radiographically.
- h. CEA, calcitonin (for patients with MTC only). Prior to Cycle 5 and 7 and then every 3rd cycle. Calcitonin measurements should be obtained in the fasting state.
- i. X-ray tibial growth plate. Prior to Cycle 5 and every 6 cycles thereafter in patients with open growth plates, follow-up plain radiographs of the same growth plate(s) should be obtained. See [Section 5.10.1](#) for details and management of growth plate toxicity.
- j. Patient diary. End of each cycle. For patient diary see [Appendix III](#).
- k. Pregnancy test. Female patients of childbearing potential require a negative pregnancy test prior to the start of each cycle; sexually active patients must use an acceptable method of birth control.

**This listing only includes evaluations necessary to answer the primary and secondary aims. OBTAIN OTHER STUDIES AS REQUIRED FOR GOOD CLINICAL CARE.**

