**7.1 End of Therapy & Follow-up**

STUDIES TO BE OBTAINED	End of Therapy
History	X
Physical Exam with VS	X
Ht, Wt, BSA	X
Performance Status	X
Pregnancy test*	X
CBC, differential, platelets	X
Urinalysis	X
Electrolytes including Ca ++ , PO 4 , Mg ++	X
Creatinine, SGPT, bilirubin	X
Total protein/albumin	X
Tumor Disease Evaluation	X

CEA and calcitonin (for patients with MTC only)	X
---	---

\*For female patients of childbearing potential.

Follow-up on this study is required at 30 days from the last date of protocol therapy, 6 months for the first year from the last date of protocol therapy and annually thereafter for up to five years from the date of study entry.

See COG Late Effects Guidelines for recommended post treatment follow-up:

<http://www-survivorshipguidelines.org/>

**Note:** Follow-up data are expected to be submitted per the Case Report Forms (CRFs).

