9.3.4 Adverse Event Monitoring Rule

We will use a Bayesian rule to monitor for protocol-specific toxicities. We will assume a beta prior distribution with  $\alpha = 0.52$  and  $\beta = 2.08$ . At least once per month, we will calculate the posterior probability (given the data) that the probability of protocol-specific toxicity exceeds the 20% threshold:

$$P(p_{\text{protocol-specific toxicities}} > 20\% | \text{Data}) = \int_{0.2}^1 \frac{\binom{n}{x} p^x (1-p)^{n-x} \frac{\Gamma(2.6)}{\Gamma(0.52)\Gamma(2.08)} p^{-0.48} (1-p)^{1.08}}{\int_0^1 \binom{n}{x} q^x (1-q)^{n-x} \frac{\Gamma(2.6)}{\Gamma(0.52)\Gamma(2.08)} q^{-0.48} (1-q)^{1.08} dq} dp$$

Here  $n$  is the number of protocol-specific toxicity-evaluable cycles and  $x$  is the number of such cycles on which a protocol-specific toxicity event is observed. Examples of situations in which this rule will indicate protocol-specific toxicities have been noted and are presented below:

Number of failures	Number of patient-cycles
2	6
3	10
4	14
5	19
6	23
7	28
8	32
9	37
10	41
11	46
12	51

13	55
14	60

Protocol-specific toxicities of interest include fatigue, headache, proteinuria, hypertension, reversible posterior leukoencephalopathy syndrome (RPLS), palmar-plantar erythrodysesthesia, oral mucositis, ALT increase, lipase increase, bilirubin increase, diarrhea, thrombocytopenia, hypothyroidism, nausea, anorexia, neutropenia, weight loss and vomiting.

If there is strong evidence (posterior probability of at least 70% with at least 2 observed toxicities) that there is a per course protocol-specific toxicity probability of more than 20%, such information will be presented to the DSMC.

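### The end-of-therapy panel omits lipase, amylase, AST and TSH, so no required draw covers the last part of a patient's final cycle and some Grade 3 or higher asymptomatic rises can be missed

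*Combined protocol and SAP*

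**What the plan says.** The on-treatment schedule thins out over time. In Cycle 1, Section 4.2.2 item d asks for "urinalysis, amylase, lipase. Prior to Cycle 1 and every 2 weeks during Cycle 1", and the delivery map places item d on Days 1 and 15. In Cycles 2 and 3, Section 4.3.2 asks for "albumin, bilirubin, urinalysis, amylase, lipase. Every 2 weeks", again on Days 1 and 15. From Cycle 4, Section 4.4.2 item d reads "bilirubin, AST, ALT, albumin, urinalysis, amylase, lipase. Day 1 of each cycle". AST belongs to item d throughout.

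TSH is item e in all three lists. The maps show it on Day 1 only, and Section 4.4.2 states "TSH. Day 1 of each cycle. Patients found to have an abnormal TSH level should have a free T4 level measured".

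The chemistry kept at end of therapy in Section 7.1 is electrolytes, total protein/albumin and "Creatinine, SGPT, bilirubin", with a blood count and urinalysis. There is no row for lipase, amylase, AST or TSH. The same section requires follow-up 30 days after the last treatment but names no laboratory test for it.

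Section 9.3.4 counts "lipase increase, bilirubin increase, diarrhea, thrombocytopenia, hypothyroidism" among its protocol-specific toxicities. Its denominator n is "the number of protocol-specific toxicity-evaluable cycles", a term that is not defined further. Section 9.5 makes a patient evaluable for toxicity after one dose. Section 11.10 limits routine adverse event reporting to Grade 3 and higher plus events reportable through CTEP-AERS.

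**The concern.** An abnormality that starts after a cycle's last draw is normally found at the next cycle's Day 1. The final cycle has no next Day 1, and the end-of-therapy panel, which could close the gap, leaves these four tests out.

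The plan itself treats the tests as needed. Each observation list says it is confined to what the primary and secondary aims require, and Aim 1.2.1 is toxicity. Lipase increase was a Cycle 1 dose-limiting toxicity in the pediatric phase 1 trial, and hypothyroidism was a frequent event there (Section 2.4.1). Section 5.8 has a specific provision for asymptomatic Grade 3 amylase or lipase elevation, and an asymptomatic rise is found only by a blood test. Section 5.7 groups ALT, AST and bilirubin, yet Section 7.1 keeps two of the three. No reason is given for the omissions.

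At stake are complete ascertainment of Grade 3 or higher laboratory events for Aim 1.2.1 and a final check on patients leaving treatment.

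**Working it through.** **1. Schedule side by side** (delivery maps and lists in 4.2 to 4.4, table in 7.1).

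| Test | Cycles 1–3 | Cycle 4 on | End of therapy | Uncovered in the final cycle |
|---|---|---|---|---|
| Lipase, amylase, AST | Days 1, 15 | Day 1 | none | after Day 15 (Cycles 1–3); whole cycle (Cycle 4 on) |
| TSH | Day 1 | Day 1 | none | whole cycle, always |
| ALT, bilirubin | Days 1, 15 | Day 1 | yes | none |

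A patient treated for one cycle has no required on-treatment TSH.

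**2. Size for lipase.** The documents give no per-cycle risk, so r = 3% for Grade 3 or higher is an assumption. With constant risk over k cycles, true risk is 1 − (1 − r)^k. Observable risk uses the covered time: k − 0.5 cycles if the last cycle is 1 to 3, and k − 1 from Cycle 4.

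- k = 2: true 1 − 0.97^2 = 5.9%; observable 1 − 0.97^1.5 = 4.5%.
- k = 4: true 1 − 0.97^4 = 11.5%; observable 1 − 0.97^3 = 8.7%.

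Both are about 24% too low in relative terms. Range over the assumed risk:

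- r = 1%: 1.5% against 2.0% (k = 2) and 3.0% against 3.9% (k = 4).
- r = 10%: 14.6% against 19.0% (k = 2) and 27.1% against 34.4% (k = 4).

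The relative shortfall stays at 21% to 25% because it mostly restates the uncovered fraction (0.5/2 and 1/4). It depends more on k. At r = 3% it is 1.5% against 3.0% for one cycle, and 28.5% against 30.6% for twelve. All of these are upper limits on the loss, since they assume no test outside the schedule.

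**3. Hypothyroidism.** Section 11.8 requires no expedited report for Grade 1 or 2 events without hospitalization. The reporting exceptions in Section 6.1 list hypothyroidism at Grade 2, and Section 11.10 starts routine collection at Grade 3. Low-grade hypothyroidism known only from TSH would mostly not reach the tables even if it were measured.

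**4. The monitoring rule.** The posterior is Beta(0.52 + x, 2.08 + n − x), flagged when P(p > 0.20) is at least 0.70. All 13 printed pairs reproduce; for example 2/6 gives 0.7001 and 2/7 gives 0.632, while 14/60 gives 0.7135 and 14/61 gives 0.691. The table is correct, and only the data fed to it are in question.

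Assume a true pooled rate of 30% per cycle, a share s of events visible only through lipase or TSH, K cycles per patient, and every last cycle counted and wholly uncovered. The observed rate is 0.30 × (1 − s/K).

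- s = 10%, K = 4: 0.2925. s = 10%, K = 2: 0.285.
- Simulated chance of a flag within 60 cycles, looking every 5: 0.956 at 0.30, 0.945 at 0.2925, 0.933 at 0.285.
- s = 25%: 0.281 (K = 4) and 0.2625 (K = 2). For the latter the flag chance lies between 0.852 (simulated at 0.255) and 0.897 (at 0.27).

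The K = 2 figures overstate the loss for lipase, which has a Day 15 draw in that cycle.

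**The case against.** The strongest reply is that unscheduled does not mean unmeasured. The observation lists invite other tests for good clinical care, and Section 7.1 still requires a history and physical examination. From Cycle 4 the map puts tumor evaluation and Day 1 chemistry at the same pre-cycle visit, and starting a cycle requires the Section 3.2.7 laboratory limits, which include amylase and lipase. A patient found to have progressed at that visit may already have had these tests. This stands and reduces the gap, but it does not close it. For example, the first on-treatment scan is mapped to the end of Cycle 2, ahead of the Cycle 3 Day 1 bloods.

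Three stronger readings are tempting, and the documents do not support them.

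- A reader might infer that an untested last cycle certainly counts in the denominator of Section 9.3.4. No text excludes it, but a toxicity-evaluable cycle is undefined, so this remains an inference.
- A reader might turn the TSH gap directly into a bias. At an assumed constant stopping chance of 20% to 50% per cycle, 20% to 50% of treated cycles have no later scheduled TSH. That is not the effect on any reported rate, because routine collection starts at Grade 3.
- A reader might conclude that the safety alert is seriously blunted. It pools 18 toxicities, most found by symptoms, blood pressure or tests kept at end of therapy; AST and amylase are not among them. One lost event can remove a flag at the boundary (4/14 gives 0.730, 3/14 gives 0.501), but the average effect is small unless lipase- or TSH-only events make up a large share.

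**Conclusion.** The gap is real and the consequence is modest. No protocol-required lipase, amylase, AST or TSH follows the last draw of a patient's final cycle. Grade 3 or higher asymptomatic rises in the first three can be missed. Those incidences are then somewhat understated for Aim 1.2.1, most for patients with few cycles, and a patient can leave treatment with an undetected abnormality. The lipase figures are an illustration resting on an assumed constant per-cycle risk and on no testing outside the schedule; the documents supply neither. The schedule facts need no assumption. The effects on tabulated hypothyroidism and on the pooled alert are small and do not carry the point. It is a cheap improvement, not a threat to the trial's conclusions.

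**What to change.** Add lipase, amylase, AST and TSH (with free T4 if TSH is abnormal) to the Section 7.1 end-of-therapy table, run on the blood already drawn there for the count and chemistry. The cost is four assays once per patient, for 146 projected patients (Section 9.7), plus an occasional free T4. There is no extra visit, and reported laboratory toxicity may rise slightly.

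Excluding last cycles without a post-dose value from the toxicity tables is not recommended. The Section 9.3 tables count each patient once at worst grade, so they contain no last cycle to remove. Restricting to tested cycles would favor symptom-driven testing and push rates upward, and it would sit badly with the one-dose rule in Section 9.5.
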